4.3.5 Post-Trial Access to Rituximab

Roche does not intend to provide rituximab or other study interventions to patients after conclusion of the study or for any early patient withdrawal.

4.4 CONCOMITANT THERAPY

Prophylactic treatment for *Pneumocystis jiroveci* should be in accordance with local, routine clinical practice. Any concomitant medications (including over-the-counter medications, herbal medications, preventive vaccines, *Pneumocystis jiroveci* prophylactic medications, vitamins, and food supplements) and procedures considered clinically relevant by the investigator must be recorded on the appropriate electronic Case Report Form (eCRF). A description of the type of drug or procedure, the amount, duration, reason for administration of drug, and the outcome of any procedure must be documented. AEs that are judged by the investigator to be related to the administration of a concomitant medication or the performance of a procedure must also be documented on the appropriate Adverse Event eCRF. It is important that dosages of medications received by patients during the remission induction phase (up to Month 6) remain stable. However, changes in treatment will be allowed as clinically required for safety reasons.

4.4.1 Glucocorticoids

Glucocorticoids other than those specified per protocol are permitted. This includes, but is not limited to, the use of inhaled glucocorticoids for participants with documented asthma and for participants with large airway involvement of GPA, as documented on bronchoscopy. Local injections of glucocorticoid into subglottic GPA lesions are also permitted. Doses of glucocorticoids other than those specified in the protocol should, whenever possible, remain stable. All use of additional glucocorticoids for all indications, including GPA and MPA, must be documented accurately on the Glucocorticoid Log.

4.4.2 Plasmapheresis (Plasma Exchange)

Patients requiring plasmapheresis at screening are not eligible to enter the study. Patients requiring plasmapheresis prior to entering the study must have completed the process 28 days prior to screening. During the study, plasmapheresis is permitted if absolutely necessary in the opinion of the investigator, to treat the patient. Plasmapheresis will alter the pharmacokinetics of rituximab, if it occurs during the initial four infusions it may reduce efficacy and should therefore be used with caution.

4.4.2.1 Treatment of GPA and MPA after Month 6

The optimal treatment after rituximab induction for GPA or MPA has not been established in adult or in pediatric patients. After Month 6, treatment for maintenance of remission should be in accordance with clinical judgment of the investigator and can include glucocorticoids, AZA, CYC, MMF, MTX, rituximab, or other therapy.

Recommended non-mandatory treatment for relapse:

Major relapse:

- Treat with CYC, rituximab, or MMF therapy, and with methylprednisolone and/or plasma exchange according to investigator's discretion, or
- Increase prednisolone or prednisone to 1 mg/kg/day; reduce to 20 mg/day by 4 weeks, and return to baseline steroid dose when remission is achieved

Minor relapse:

- Increase prednisolone or prednisone to 0.5 mg/kg/day then reduce to baseline steroid dose over 1 month

Relapsing patients will remain in the study and all changes in drugs and doses are to be recorded in the eCRF.

Patients who are protocol remission failures or experience disease flare that cannot be controlled by glucocorticoids alone should receive treatment in accordance with local standard of care at the discretion of the investigator and will remain in the study, with all changes in drugs and doses to be recorded in the eCRF.

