3.3.2 Rationale for Patient Population

Children ages 2 to 11 years and adolescents ages 12 to < 18 years will be included in the trial, since the safety and effectiveness of rituximab in pediatric patients with GPA and MPA have not been studied.

Inclusion of patients <2 years old is not considered appropriate on the grounds of safety with respect to the immaturity of the immune system of young children and the risks this could present following treatment with rituximab. Although younger children (i.e., ages 2–6 years) may not have completed their childhood vaccination program, given the severity of GPA and MPA, the potential risk–benefit is considered appropriate so as to include this subset in the clinical trial. Moreover, standard treatment of pediatric GPA and MPA is broadly similar to that in adults (immunosuppression with CYC followed by maintenance of remission with AZA or MTX), which in some cases could be in the context of non-completion of childhood vaccination programs.

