4.1.1 Inclusion Criteria

Patients must meet the following criteria for study entry:

- Written informed consent for study participation obtained from patient's parents or legal guardian, with assent as appropriate by the patient, depending on the patient's level of understanding
- Age at screening between ≥ 2 and < 18 years
- Diagnosis of GPA (EULAR/PRINTO/PRES 2008, Ankara criteria for childhood WG [Özen et al. 2010]; see [Appendix 5](#)) or diagnosis of MPA (according to the Chapel Hill Consensus Conference [Jennette 1994]; see [Appendix 6](#))
- Newly diagnosed patients or patients with relapsing disease according to the following definition:
 - The recurrence or new onset of potentially organ- or life-threatening disease (i.e., one or more major BVAS/WG items listed in [Table 3](#) or disease severe enough to require treatment with CYC).
- For patients of reproductive potential (males and females), use of a reliable means of contraception (e.g., abstinence, hormonal contraceptive patch, intrauterine device, physical barrier) throughout their study participation

- For all eligible patients, mandatory prophylactic treatment for *Pneumocystis jiroveci* infection

Table 3 BVAS/WG Features of Limited and Severe AAV

Severe (Major) BVAS/WG Items ^a	Limited (Minor) BVAS/WG Items ^b
Cutaneous gangrene	Arthralgias/arthritis
Scleritis	Fever (> 38°C)
Retinal exudates/hemorrhage	Purpura
Sensorineural hearing loss	Skin ulcer
Mesenteric ischemia	Mouth ulcers
Alveolar hemorrhage	Conjunctivitis/episcleritis
Red blood cell urinary casts	Orbital mass/proptosis
Rise in serum creatinine 30% over baseline value	Uveitis
Aseptic meningitis	Bloody nasal discharge/nasal crusting
Spinal cord lesions	Sinus involvement
Cerebrovascular accident caused by vasculitis	Swollen salivary gland
Cranial nerve palsy	Subglottic inflammation
Sensory peripheral neuropathy	Conductive deafness ^c
Motor mononeuritis multiplex	Pericarditis
	Pleurisy
	Pulmonary nodules or cavities
	Other pulmonary infiltrates secondary to vasculitis
	Endobronchial lesions
	Hematuria

AAV=ANCA-associated vasculitis; ANCA=anti-neutrophil cytoplasmic antibody
 BVAS=Birmingham Vasculitis Activity Score; WG=Wegner's granulomatosis.

^a Any of these items must be attributable to the active underlying disease.

^b Minor items with a significant risk of morbidity may be classified as severe (i.e., BVAS/WG 3).

^c Additional testing may be required to make the diagnosis.

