4.3.2.3 Prednisolone or Prednisone (Non-Investigational Medicinal Product)

4.3.2.3.1 Dosage, Administration, and Compliance

On Day 1 and following completion of IV glucocorticoids, all patients will receive concomitant oral prednisolone or prednisone (1 mg/kg/day or up to 60 mg/day or equivalent, whichever is lower), the dose of which will be tapered to a minimum of 0.2 mg/kg/day (or 10 mg/day, whichever is the lowest) no later than Month 6.

The general guidance on the suggested oral steroid dose-tapering schedule is to taper from 1 mg/kg/day (60 mg/day, maximum) at the start of treatment, to 0.8 mg/kg/day by Month 1, and then by 0.1–0.2 mg/kg/day each month to 0.2 mg/kg/day (or 10 mg/day, whichever is the lowest), which should be reached no later than Month 6.

Oral prednisone (used in some non-UK sites) may be substituted for prednisolone at the same dose as long as there is no hepatic impairment.

The steroid-tapering practice is specific to a particular patient and as such should be tailored individually for each patient at the time of study entry, at the discretion of the investigator.

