4.5.3.5 Laboratory Assessments

The following laboratory tests will be recorded at the time points indicated in the schedule of assessments (see [Appendix 1](#)). Whenever possible, laboratory samples should be drawn in the morning. Unscheduled laboratory assessments for safety issues are permitted at any time.

With the exception of samples for rituximab and HACA levels (for PK/PD assessments) obtained according to the schedule of assessments, all laboratory assessments requiring a blood sample are to be performed as part of routine clinical care.

The total volume of blood loss for laboratory assessments (including all safety, efficacy, PK/PD, and immunologic assessments) does not exceed the per-visit and per-cumulative visit recommendations made by the University of Pittsburgh's Institutional Review Board (IRB) and the NIH for the expected average weights of the patient. However, if the enrolled patient weighs < 13 kg, please check with the Roche Medical Monitor for planning the blood draws. This weight is based on acceptable blood draw limits of 2 mL/kg (blood draw in a day) or 4 mL/kg (blood draw in a month) at Children's Hospital Seattle.

The procedures for the collection, handling, and shipping of laboratory samples are specified in the Sample Handling and Logistics Manual supplied to sites.

The samples for this study should be classified, packed, and shipped as UN3373 Biological Substance, Category B.

Local Laboratory Assessments

Samples for the following laboratory tests will be sent to the study site's local laboratory for analysis:

- Serum ANCA sample: ANCA testing performed at the screening visit may be performed locally or centrally. All other ANCA testing should be performed centrally.
- Acute-phase reactants: erythrocyte sedimentation rate and C-reactive protein
- Urinalysis: dipstick for blood, protein, and glucose, and albumin to creatinine ratio
- Pregnancy test: urine dipstick test for all females of childbearing potential

Central Laboratory Assessments

Samples for the following laboratory tests will be sent to one or several central laboratories or to the Sponsor for analysis. Instruction manuals and supply kits will be provided for all central laboratory assessments.

- Serum ANCA sample: ANCA testing performed at the screening visit may be performed locally or centrally. All other ANCA testing should be performed centrally.

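### The optional oral-steroid taper for major relapse (Protocol 4.4.2.1) gives no usable 4-week reduction step for children of 20 kg or less

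*Protocol*

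**What the plan says.** Protocol Section 4.4.2.1 covers treatment after Month 6. Under the label "Recommended non-mandatory treatment for relapse" it gives two options for major relapse. The first is cyclophosphamide, rituximab or mycophenolate, with methylprednisolone and/or plasma exchange at the investigator's discretion. The second is oral: "Increase prednisolone or prednisone to 1 mg/kg/day; reduce to 20 mg/day by 4 weeks". The same sentence ends by returning the child to the baseline steroid dose once remission is reached.

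Other oral-steroid rules in the protocol are built differently:

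- Minor relapse, same section: "Increase prednisolone or prednisone to 0.5 mg/kg/day then reduce to baseline steroid dose over 1 month". There is no fixed-mg target.
- Induction start, Section 4.3.2.3.1: "1 mg/kg/day or up to 60 mg/day or equivalent, whichever is lower".
- Induction taper, same section: 0.8 mg/kg/day by Month 1, ending at the lower of 0.2 mg/kg/day and 10 mg/day by Month 6.

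On who can enter, Section 4.1.1 requires "Age at screening between ≥ 2 and < 18 years", and neither 4.1.1 nor 4.1.2 sets a minimum weight. For children aged 2 to 6, Section 3.3.2 says the risk–benefit "is considered appropriate so as to include this subset in the clinical trial". Section 4.5.3.5 has a blood-draw instruction that begins "However, if the enrolled patient weighs < 13 kg".

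**The concern.** The relapse course begins with a dose proportional to weight and then names a milligram figure that is the same for every child. In a trial open from age 2, such a figure can stop being a reduction. For a light enough child the instruction to reduce has no 4-week dose that satisfies it.

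What is at stake is the guidance for the smallest children in the only oral schedule with numbers for major relapse. If the printed step cannot be used, nothing in the sentence moves the child off 1 mg/kg/day between the start and remission, so full-dose steroid may run longer than a taper was meant to allow.

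**Working it through.** **Inputs.** Start: 1 mg/kg/day (4.4.2.1). Printed 4-week target: 20 mg/day (4.4.2.1). Let w be the body weight in kg at the time of relapse.

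**Formulas.** Start = 1 × w mg/day. Change from start to target = 20 − w mg/day, or (20 − w)/w as a proportion. The target is a reduction only if 20 − w < 0, that is w > 20. The break-even weight is 20 mg ÷ 1 mg/kg = 20 kg.

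| Weight (kg) | Start (mg/day) | Printed target (mg/day) | Target minus start |
|---|---|---|---|
| 12 | 12 | 20 | +8 (+67%) |
| 15 | 15 | 20 | +5 (+33%) |
| 18 | 18 | 20 | +2 (+11%) |
| 20 | 20 | 20 | 0 |
| 22 | 22 | 20 | −2 (−9%) |
| 25 | 25 | 20 | −5 (−20%) |
| 30 | 30 | 20 | −10 (−33%) |
| 40 | 40 | 20 | −20 (−50%) |

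The protocol states no derived figure here, so there is nothing to reproduce. The check is a comparison of two printed doses.

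**Does another section supply the missing limit?** No.

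- The lower-of-two rules in 4.3.2.3.1 govern the induction dose and its taper, not a relapse after Month 6.
- The same section says tapering is to be "tailored individually for each patient at the time of study entry". That ties it to entry, and it names no relapse dose.
- The clinical-judgment sentence in 4.4.2.1 is about maintaining remission. The closing paragraph of 4.4.2.1 is about remission failures and flares that glucocorticoids alone cannot control. Neither gives a 4-week figure.

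**Size of the gap on the likely reading.** If a small child simply stays at 1 mg/kg/day, the protocol's own Month 1 induction level of 0.8 mg/kg/day is a fair yardstick. The excess is 0.2 × w: 2.4 mg/day at 12 kg (12 against 9.6), 3 mg/day at 15 kg (15 against 12) and 4 mg/day at 20 kg (20 against 16).

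**The case against.** A reader might infer that the protocol directs a steroid increase in small children, since 20 mg/day is 1.67 mg/kg/day at 12 kg. The documents do not support that. The verb is to reduce, and a prescriber whose patient is already on 12 or 15 mg/day would ordinarily take the level as met. Raising the dose would mean acting against the instruction.

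The rest of the case against the point concerns weight rather than correctness:

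- The guidance is optional, and this is the second of two options. The first has no such gap.
- Section 4.4.2.1 says the best treatment after induction is not established, and Section 4.4.1 permits glucocorticoids beyond those specified.
- The return to baseline dose at remission works at every weight, so only one intermediate step is lost.
- Exposure requires a child still at or below 20 kg when a major relapse occurs after Month 6, and an investigator who chooses the oral option. The under-13-kg instruction shows that such weights were allowed for, not that they were expected.

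All of this stands, and it limits the consequence. It does not remove the fault: guidance that gives a number should give one that works across the eligible range.

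**Conclusion.** The point holds as a minor dosing fault, wrong as written. For children of 20 kg or less, the 4-week target in the oral major-relapse option is not a reduction. The likely result is a missing taper step, with the child possibly held at 1 mg/kg/day until remission.

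The 20 kg threshold is exact and depends only on the two printed doses. The consequence rests on the assumption that investigators follow the verb rather than the number. The documents give no weight distribution, so how many of the at least 25 planned patients could be affected cannot be stated and may be none. The sample size, the safety and PK objectives and the planned analyses are untouched.

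**What to change.** Amend the step to read: *reduce to 20 mg/day or 0.8 mg/kg/day, whichever is lower, by 4 weeks*. The 0.8 figure is the Month 1 level already in Section 4.3.2.3.1, and the sponsor's clinicians should confirm it for relapse.

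Check: the new target is min(20, 0.8w). It is never above 0.8w, so it is below the start w at every weight. It gives 0.8 × 12 = 9.6 mg/day at 12 kg, 12 at 15 kg, 14.4 at 18 kg and 16 at 20 kg. It reaches 20 mg/day at 20 ÷ 0.8 = 25 kg and leaves the printed dose unchanged from there up.

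Two alternatives are less good:

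- A limit of 0.5 mg/kg/day, the minor-relapse starting dose, would also work. But it would lower the 4-week dose for all children between 20 and 40 kg (30 kg: 15 instead of 20 mg/day), where the printed step is already a reduction.
- A clause leaving children of 20 kg or less to the investigator would touch no one else, but would still give them no figure.

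Costs:

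- Children between 20 and 25 kg get a slightly lower 4-week dose (22 kg: 17.6 instead of 20 mg/day).
- The text amendment needs IRB/EC approval and, where locally required, regulatory approval before use (Protocol 9.5). There is no data or visit cost.
- SAP Section 4.3 (output DS201SP) records the common closeout date as 10 May 2018, so the change helps this trial's patients only if made before then.

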4.4.3 Vaccinations

4.4.3.1 Passive Antibody Titers to Specific Antigens

Review of long-term safety data from patients with RA exposed to rituximab shows that rituximab does not appear to have an effect on specific humoral immunity to several common bacterial and viral antigens over the observation period, including repeat treatment courses. The proportions of patients with positive antibody titers against mumps, rubella, varicella, tetanus toxoid, influenza, and *Streptococcus pneumoniae*, post-rituximab were similar to the proportions at baseline.

4.4.3.2 Immunization and Humoral Responses to Clinically Relevant Vaccines

In a randomized, controlled study of immunization responses (SIERRA) ([Bingham et al 2008](#)), patients with RA who were peripherally depleted of B cells and receiving rituximab + MTX had effective humoral responses to recall antigen (tetanus toxoid) administered 6 months after rituximab, similar to the responses observed in patients receiving MTX alone. Some rituximab-treated patients mounted T-cell-independent responses to the 23-valent pneumococcal polysaccharide vaccine but responses were decreased overall compared with those in patients receiving MTX alone. Because polysaccharide vaccines elicit a T-cell-independent response, and rituximab targets peripheral CD20⁺ B cells, decreased responses to polysaccharide vaccines are consistent with the mechanism of action of rituximab. Although responses to the 23-valent pneumococcal polysaccharide vaccine were decreased, a significant number of patients were able to mount positive responses. For example, a total of 57% and 43% of patients had at least a 2-fold increase in titers to at least one or two pneumococcal serotypes, respectively.

It is recommended that a patient's vaccination record and the need for immunization be carefully investigated in all patients prior to entering the study or receiving a further course of rituximab. If vaccination is necessary, it is recommended that any required vaccination or booster be given at least 28 days prior to the first infusion of rituximab. The use of live or attenuated vaccines (i.e., measles, mumps, rubella, oral polio, Bacille Calmette Guerin [BCG], typhoid, yellow fever, vaccinia, some forms of influenza [e.g., FluMist[®]] or any other live vaccines not yet licensed but belonging to this category) are specifically prohibited during the study and while the patient's peripheral B-cells are depleted.

The use of killed or inactivated vaccine (e.g., some forms of influenza) is not prohibited during the study; however, the efficacy of certain vaccines during or following periods of B-cell depletion has not been studied in this patient population.

Patients who are eligible for yearly influenza vaccine or who require other non-live booster vaccinations can receive vaccination with killed or toxoid vaccines in accordance with normal clinical practice.

There is no planned analysis of antibody titers to common vaccinations. If clinically indicated, additional analysis of the immune status of patients may be considered using serum samples already collected for other protocol-defined analyses.

4.4.4 Prohibited Therapy

Treatment with any investigational agent, cell-depleting therapy (except for CYC and rituximab), or biologic agents such as TNF antagonists, anti- α 4 integrin antibody, or co-stimulation modulator, is prohibited during the main study (until common closeout date). Any patients who do receive a prohibited therapy or any GPA or MPA treatment other than protocol-defined glucocorticoids will remain in the study for follow-up.

Thereafter (i.e., at time points after the receipt of prohibited therapy or any GPA or MPA treatment other than protocol-defined glucocorticoids), patients will be considered to have failed to meet the protocol-defined remission endpoints, irrespective of BVAS/WG and PVAS scores.

Guidelines for dosage modification and treatment interruption or discontinuation are provided in Section [5.2.3](#).

4.5 STUDY ASSESSMENTS

The sequence of assessments at each visit will be standardized as follows (at visits required by the schedule of assessments) and should be performed prior to infusion, with the exception of the post-dose PK sample.

1. PRO assessments: [REDACTED]
2. Efficacy assessments: [REDACTED], and per schedule of assessments (see [Appendix 1](#))
3. Laboratory samples: All samples (including for safety and efficacy) must be obtained prior to study drug treatment, except for some samples for PK analysis, which will be obtained after study drug treatment. The laboratory samples can be drawn either at least 30 minutes before or at any time after the nurse or investigator assessments.
4. Safety assessments: review of AEs, vital signs, concomitant medications, and laboratory data
5. Post-dose PK sample (at scheduled visits, where indicated). The post-infusion PK sample should be taken from the opposite arm to that into which the rituximab infusion was administered.

4.5.1 Medical History and Demographic Data

Medical history includes life-long clinically significant diseases, surgeries, birth and developmental history, cancer history (including cancer therapies and procedures), smoking history, use of alcohol and drugs of abuse, immunization history, and all previous and current clinically relevant concomitant medications (e.g., prescription drugs, over-the-counter drugs, herbal/homeopathic remedies, nutritional supplements)

used by a patient within 365 days prior to the screening visit, except for the history of use of medications for GPA or MPA (e.g., CYC, AZA, MTX, glucocorticoids) when all available data should be recorded.

Demographic data will include age, sex, and patient- or parent/guardian-reported race/ethnicity.

4.5.2 Efficacy Assessments

[REDACTED]

4.5.2.1

[REDACTED]

[REDACTED]

4.5.2.2

[REDACTED]

[Redacted]

4.5.2.3 [Redacted]

[Redacted]

4.5.2.4 [Redacted]

4.5.2.5 Patient-Reported Outcomes

[Redacted]

[REDACTED]

4.5.3 Safety Assessments

4.5.3.1 Vital Signs

Vital signs (i.e., pulse rate, systolic and diastolic blood pressure, and temperature) will be taken at the times indicated in the schedule of assessments (see [Appendix 1](#)). Assessments will be taken after the patient has been in a semi-supine position for at least 5 minutes. Blood pressure measurements should be obtained using a child-appropriate cuff size.

